1 BACKGROUND AND RATIONALE

The major goals of the project are:

Aim 1: To estimate the influence of informational nudges on the engagement of primary care providers in an opioid treatment learning collaborative to address the opioid overdose crisis. Primary care providers in North Carolina, including physicians, nurse practitioners, and physician assistants, will be randomly assigned to receive either a pro-social recruitment approach for participating in the UNC ECHO MAT intervention or standard recruitment practice. Treatment assignment will provide pro-social information, including customized figures on the opioid use epidemic in the provider's region and the degree of the provider shortage in their region. The comparison arm will include a standard approach to recruitment that does not contain a pro-social recruitment message. Analysis of this data will provide estimates of the degree of responsiveness of providers to informational nudges.

Aim 2: To estimate the influence of financial incentives on the participation intensity of primary care providers in an opioid treatment learning collaborative to address the opioid overdose crisis. At the second stage, providers agreeing to enroll in the program will be re-randomized to one of three levels of reimbursement for time spent participating in the UNC ECHO MAT intervention. Analysis of this data will provide causal estimates of the degree of responsiveness of provider participation intensity to financial incentives. A sub-aim will examine whether the effect of incentives on participation intensity varies between the pro-social recruitment group and status-quo recruitment group. The results from this study will inform the feasibility and design of a full-scale trial testing the effects and cost-effectiveness of approaches to address the shortage of adequately trained primary care clinicians, providing urgently needed information on best practices in developing the health care workforce to treat individuals and communities most affected by the opioid crisis.

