2.2 Secondary Objective

A sub-aim will examine whether the effect of incentives on participation intensity varies between the pro-social recruitment group and status-quo recruitment group.

3 INVESTIGATIONAL PLAN (brief overview)

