Phase 1: Primary care providers will be randomized by practice to 1 of 4 study arms. Computerized randomization will assign practices to study arms, practices and primary care providers will have an equal chance of being randomized to each study arm.

Phase 2: Eligible participants will be randomized to the Phase 2 study arm upon enrollment in the study. Randomization will be assigned using a predetermined randomly ordered list of study condition assignments. Upon enrolling in the study, the participants will be assigned to the condition that is next on the list. Participants will have an equal chance of being randomized to each study arm.

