6 STATISTICAL CONSIDERATIONS

6.1 Statistical Methods

In Aim 1, we anticipate starting with a random selection of 600 providers from the list of eligible NC providers received from the NC Board of Medicine and NC Nursing Board, limiting to primary care providers identified as primary care through their provider type, which gives more than 90% power to detect a ten percentage point difference in the binary outcome, response to study recruitment. We will use binary models (logit, linear probability models) to examine response to recruitment as a function of study arm, controlling for provider type and county fixed effects.

For Aim 2, we will randomly recruit at least 60 enrollees (and up to 80 to enroll at least 20 providers per arm of this phase). The outcome to be monitored for Aim 2 is the number of ECHO sessions attended in the 6 months following randomization. Because this is a pilot study, the sample size is not powered for the primary outcome, number of ECHO clinics attended. We will conduct a negative binomial or other count data model (depending on statistical tests) of the number of sessions as a function of financial incentive arm to estimate the effect of financial incentives on participation.

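### Phase 2 uses one list with no stated strata or blocks, so the payment-arm split within each recruitment-letter group, which the sub-aim needs, is left to chance; the loss is modest and cheap to avoid

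*Combined protocol and SAP*

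**What the plan says.** Section 3.1 (Randomization, Phase 2) describes one allocation source: "Randomization will be assigned using a predetermined randomly ordered list of study condition assignments". It is used in order of enrolment: "Upon enrolling in the study, the participants will be assigned to the condition that is next on the list". The ratio is even: "Participants will have an equal chance of being randomized to each study arm". The document mentions neither blocks nor stratification by recruitment letter for this list. It does not say in words that the letter is ignored; that follows from the single list and the silence on strata.

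Section 2.2 sets the secondary objective, which Section 1 also states: "A sub-aim will examine whether the effect of incentives on participation intensity varies between the pro-social recruitment group and status-quo recruitment group".

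On size, Section 6.1 says "we will randomly recruit at least 60 enrollees (and up to 80 to enroll at least 20 providers per arm of this phase", and adds: "Because this is a pilot study, the sample size is not powered for the primary outcome, number of ECHO clinics attended". It gives no interaction model and no target for the cells of the sub-aim. Section 8 describes four recruitment letters in a 2 x 2 layout, whereas the sub-aim names two groups.

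**The concern.** The sub-aim compares payment-arm differences between two letter groups, so all three arms must be adequately represented in each group. The letter is fixed in Phase 1, before Phase 2 assignment, and could be used at that point. As written, it is not.

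Aim 1 tests whether the pro-social letter changes response. If it does, one letter group will be the smaller, and its division over three arms is then uncontrolled. A list balanced over all enrollees does not prevent this, and a letter term in the model cannot restore a nearly empty cell. At stake is the precision of the interaction, already the least precise quantity in the study, and in the tail whether one arm can be assessed at all in the smaller group.

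**Working it through.** **Inputs from the document.** Three arms at equal chance (3.1); at least 20 per arm, hence 3 x 20 = 60, which reproduces the stated minimum, and up to 80 (3.3, 6.1); two letter groups (2.2).

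**Assumptions, not in the document.** The split of enrollees by letter group (even, one third or one quarter in the smaller group); equal SD in all cells; two-sided 5% test and 80% power. The outcome is treated as approximately normal to give a scale.

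**Formula.** For arms a and b and letter groups 1 and 2, the interaction contrast has variance SD² x (1/n_a1 + 1/n_b1 + 1/n_a2 + 1/n_b2). The benchmark is an even split of arms within each letter group.

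- N=60, 30/30: 4/10 = 0.40, SE 0.63 SD.
- N=60, 15/45: 2/5 + 2/15 = 0.533, SE 0.73 SD.
- N=80, 40/40: 4/13.33 = 0.30, SE 0.55 SD.

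**Increase from chance imbalance.** For a letter group of size m, the cell count has squared coefficient of variation 2/m on an unrestricted list, and (2/m) x (N - m)/(N - 1) on a list balanced overall. To second order this is the relative increase in the mean of 1/n. At N=60 and 30/30: 2/30 = 6.7%, and (2/30) x (30/59) = 3.4%. Simulated cell counts (60,000 draws) give slightly more, because 1/n is skewed. The table shows simulated values, with the variance increase averaged over the three arm pairs. The last two columns give the chance that some arm has 2 or fewer enrollees in the smaller letter group.

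| N and letter split | Mean increase, balanced list | Mean increase, unrestricted list | 2 or fewer, balanced | 2 or fewer, unrestricted |
|---|---|---|---|---|
| 60: 30/30 | 4% | 8% | 0% | 0.2% |
| 60: 20/40 | 6% | 11% | 2% | 5% |
| 60: 15/45 | 11% | 16% | 15% | 24% |
| 80: 40/40 | 3% | 6% | 0% | about 0% |
| 80: 20/60 | 8% | 11% | 3% | 5% |

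At N=80 a balanced list holds 27, 27 and 26. For the pair of arms with 27 each, the increases are 1% (40/40) and 6% (20/60), slightly below the averages shown.

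**Effect on the detectable difference.** Multiply the SE by 1.96 + 0.84 = 2.80.

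- N=60, 30/30: 2.80 x 0.632 = 1.77 SD with perfect balance; 1.77 x √1.04 = 1.81 (balanced list); 1.77 x √1.08 = 1.84 (unrestricted).
- N=60, 15/45: 2.80 x 0.730 = 2.04 SD with perfect balance; 2.04 x √1.11 = 2.15; 2.04 x √1.16 = 2.20.

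**Which rows are plausible.** Under unrestricted draws, all three arms reach 20 at N=60 with probability only 1.4% (exact multinomial), and at N=80 with probability 87%. The 20-per-arm rule therefore makes an unrestricted list that stops at 60 very unlikely.

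**After the change.** With blocks of 3 within letter group, every cell is 10 at N=60 and 30/30, the smallest cell is 13 at N=80 and 40/40, and the variance increase is about zero. At N=60 the smallest cell is 6 for 20/40 and 5 for 15/45. Separate lists without blocks gain nothing: the mean increase at N=60 and 30/30 stays at 8%.

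**The case against.** The strongest reply is that this is a pilot, declared unpowered even for its primary outcome, and that the sub-aim is secondary. With perfect balance at N=60 and an even letter split, the difference in effects would have to be about 1.77 SD for 80% power, and imbalance moves that only to 1.81 or 1.84. Not stratifying a small pilot for such a comparison is defensible, and Section 6.1's lack of any interaction analysis is the larger gap. All of this stands and sets the weight of the point: a cheap improvement, not a flaw in validity.

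A reader might infer from the 24% figure that a nearly empty cell is a likely result. The document does not support that. The figure needs unrestricted draws, enrolment stopping at 60 and a 15/45 letter split together. The 20-per-arm rule makes the first two very unlikely in combination, and no section gives a letter split. Section 3.1 gives each letter an equal chance, so about half of those contacted receive a pro-social letter, and 15/45 would require a threefold difference in enrolment rates. At N=80 with the same one-quarter share the unrestricted figure is 5%; for totals between 60 and 80 it lies in between.

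A reader might also infer that separate lists would cure the sub-aim at no cost. They help only if blocked, and they cannot control how many enrol from each letter group.

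**Conclusion.** The point holds as a modest loss of precision that can be avoided cheaply. The sub-aim needs six filled cells, and the stated allocation balances them only by chance although letter group is known at assignment.

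At an even letter split the average cost is a few percent of the interaction variance (3% to 8% over the two list types and N of 60 to 80). With one letter group at a quarter of enrollees it is about 8% to 16%. The case for acting rests mainly on the tail in that second situation, where a payment arm may have two or fewer enrollees in the smaller group and no analysis can repair it.

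These sizes rest on the assumed letter split, on equal variances, and on reading the silence about blocks and strata as their absence. The document does not support reading this as bias: allocation is random under either scheme. Nor is the list what makes the sub-aim imprecise; the small sample does that under any allocation.

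**What to change.** 1. In Section 2.2, state which of the four letters in Section 8 form the status-quo group: both letters without pro-social content, or only the recruitment-as-usual letter. The lists cannot be prepared until this is settled.
2. In Section 3.1, replace the single Phase 2 list with two, one per letter group, each in permuted blocks of varying size (3 and 6), and assign each enrollee from the list of his or her group. Chances per arm are unchanged.

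The cost is two lists instead of one. Incomplete blocks can leave an arm at 18 or 19 when N=60, which the existing allowance of up to 80 covers. Short blocks are somewhat more predictable to staff; varying the block size limits this.

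The text on the extension after 3/9/2020 suggests that participants were already in follow-up. If enrolment is complete, the change applies only to the full-scale trial that, according to Section 1, this pilot is meant to inform.

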3.2 Allocation to Treatment Groups and Blinding (if applicable)

Participants are randomized to receive 1 of 4 recruitment materials. Once enrolled, participants are then randomized to receive 1 of 3 financial reimbursements for attendance in ECHO sessions

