3.3 Study Duration, Enrollment and Number of Subjects

Each subject's participation will last six months (nine months for subjects who did not complete as of 3/9/2020 due to the complex practice environment experienced by providers during the start of the COVID-19 pandemic).

The entire study is expected to last up to two years.

Total number of subjects will be up to 80 as needed to achieve at least 20 subjects in each of the 3 financial reimbursement groups.

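### The plan does not say how the Phase 2 list is built: 20 per arm at 80 depends on that, and an unblocked list leaves the 6/9-month follow-up mix to chance, with no term for it in the count model

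*Combined protocol and SAP*

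**What the plan says.** Section 3.1 gives the whole Phase 2 allocation procedure. On the list itself it says only this: "Randomization will be assigned using a predetermined randomly ordered list of study condition assignments". Each new enrollee takes the first unused entry, and the arms are to be equally likely.

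Section 3.2 confirms three arms. Blocks, strata, list length and fixed arm totals are neither stated nor excluded anywhere.

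Section 3.3 sets the number of subjects at "up to 80 as needed to achieve at least 20 subjects in each of the 3 financial reimbursement groups". Section 6.1 adds a floor: "at least 60 enrollees (and up to 80 to enroll at least 20 providers per arm of this phase". Nothing says what happens if an arm is still below 20 at 80.

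Appendix Table 1 makes the number of sessions attended the Phase 2 primary outcome, counted over 6 months, or over 9 months for participants who had not completed by 3/9/2020. Section 6.1 models the count as a function of incentive arm and names no term for window or enrolment date. It also says that the sample is not powered for this outcome.

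**The concern.** Two properties of the design depend on how the list was made.

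The first is arm size. The minimum of 20 per arm is a stated target, and whether it is assured at the cap depends on whether list entries are independent draws, a shuffle of fixed totals, or permuted blocks.

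The second is balance over time. Enrolment date determines whether a participant is counted over 6 or 9 months. A list that is not balanced as it fills can give one arm more late enrollees, and so more observation time, than another. With about 20 per arm and a raw session count, that difference would be mixed with the incentive effect that section 2.1 aims to estimate causally.

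**Working it through.** **Inputs.** Three arms with probability 1/3 each (sections 3.1, 3.2); at least 20 per arm, floor 60, cap 80 (sections 3.3, 6.1); window of 6 or 9 months (Appendix Table 1). The documents do not give the share of participants with 9 months, so it is varied from 10% to 90%.

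**The plan's own figures.** The floor reproduces: 3 × 20 = 60. The cap of 80 has no stated derivation or target probability, so it can be neither reproduced nor called wrong.

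**Arm size, independent draws.** P(N) = Σ N!/(a! b! c!) / 3^N over all a, b, c ≥ 20 with a + b + c = N. At N = 60 there is one term, 60!/(20!)³/3^60 = 0.0136.

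| N | P(all arms ≥ 20) |
|---|---|
| 60 | 1.4% |
| 70 | 51.9% |
| 75 | 74.2% |
| 80 | 87.5% |

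The chance of missing the target at the cap is 100% − 87.5% = 12.5%. If enrolment stops once every arm has 20, or at 80, mean enrolment is Σ [1 − P(n)] for n = 0 to 79, which is 70.8. That is 10.8 beyond 60. At N = 80 the smallest arm is at least 18 in 96.2% of lists and averages 22.3.

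**Arm size, fixed totals.** A shuffled 20/20/20 list gives the target at 60 with none extra. A shuffled 27/27/26 list gives it with certainty by 80, since every total exceeds 20. Its mean stopping point is 64.3, about 4 extra.

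**Arm size, permuted blocks.** Blocks of 3 (20 blocks × 1 per arm) or of 6 (10 blocks × 2 per arm) give 20/20/20 at 60. With sizes 3 and 6 mixed at random, a block of 6 can begin after participant 57, when each arm has 19. Arms then hold 19 to 21 at 60, and all reach 20 by participant 62 at the latest.

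**Balance of the window.** Take 60 enrollees, of whom the last k have 9 months. The gap is the largest minus the smallest arm share with 9 months. For the shuffled list the probability is exact: Σ C(20,a) C(20,b) C(20,c) / C(60,k) over a + b + c = k with largest minus smallest count ≥ 4, since 4/20 = 0.20. The other columns are simulated.

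| Assumed 9-month share | Simple list, gap ≥ 0.20 | Shuffled 20/20/20, gap ≥ 0.20 | Blocks of 6, or mixed 3 and 6 |
|---|---|---|---|
| 10% | 10% | 15% | 0% |
| 25% | 34% | 40% | 0% |
| 50% | 44% | 50% | 0% |
| 75% | 34% | 40% | 0% |
| 90% | 10% | 15% | 0% |

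Between these points the shuffled figure peaks at 52% (29 or 31 of 60). The largest gap at the shares checked was 0.10 with blocks of 6 and 0.19 with mixed blocks.

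**What a gap of 0.20 could do.** As an illustration, assume a constant attendance rate per month, so that 9 months yields 1.5 times the 6-month count. Arms with shares 0.60 and 0.40 then have relative means (0.40 + 0.60 × 1.5) / (0.60 + 0.40 × 1.5) = 1.30/1.20 = 1.083, an 8% difference with no incentive effect. The extension was made because fewer sessions were held, so the true difference could be smaller.

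**The case against.** A reader might infer that the list has no blocks and that the design therefore lacks the stated arm size. The argument is that a 60-to-80 range is pointless if a blocked list reaches 20/20/20 at 60. The documents do not support that step. Section 3.1 is silent on construction, and its wording fits a blocked list or a shuffle of fixed totals as well as independent draws. The cap is not explained, and section 4.1 allows withdrawal, so a balanced list could also carry a margin. Nor does being unblocked produce the 12.5% figure: that needs independent entries, and an unblocked shuffle with fixed totals meets the target by 80.

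Further points on the plan's side are fair:
- Twenty per arm is not tied to power, shortfalls would be small, and a few extra enrollees in a minimal-risk estimation pilot do no harm.
- Chance imbalance under valid randomization is not bias.
- The 9-month share is assumed here.
- Section 6.1 mentions only 6 months after randomization, which could suggest a common window. Appendix Table 1, however, defines the outcome over the extended period, and late enrollees would have had fewer sessions on offer in any case.
- The text on 3/9/2020 suggests that enrolment may be over.

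These points lower the importance and shift the remedy towards the analysis. They leave two gaps open: the list's construction is unstated, and neither unblocked list balances enrolment over time while the planned model does not account for it.

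**Conclusion.** The concern holds in conditional form. If entries are independent one-in-three draws, at least 20 per arm is reached at 80 with probability 87.5%, and about 10.8 enrollees beyond 60 are needed on average, assuming enrolment stops when the target is met. If the list is a shuffle of fixed totals, the target is assured within 80, with 0 (20/20/20) to about 4 (27/27/26) extra. The documents do not settle which applies, so it cannot be said that the plan's arm size is unattainable or that the list is unblocked.

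The window imbalance is the more useful part, because it applies to both unblocked lists. It rests on the assumed 9-month share and on 60 enrollees. Since Phase 2 is an unpowered pilot, this is a cheap improvement of modest importance.

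**What to change.** State how the Phase 2 list was generated (independent draws, fixed totals or blocks) and what happens if an arm is below 20 at 80.

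For any assignments not yet made, use concealed permuted blocks of mixed size 3 and 6. State that 60 enrollees then give about 20 per arm, and keep 80 as a ceiling. The cost is regenerating the unused part of the list. The downside is slightly more predictable assignment, limited by the mixed sizes and concealment.

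If enrolment is complete, report realised arm sizes and the number of 6- and 9-month participants by arm, and add follow-up window or enrolment period to the section 6.1 count model, as a covariate or exposure offset. Because fewer sessions were held during the extension, an offset based on sessions offered in each participant's window is safer than one based on months. The cost is about one model term and one descriptive table.

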3.2 Allocation to Treatment Groups and Blinding (if applicable)

Participants are randomized to receive 1 of 4 recruitment materials. Once enrolled, participants are then randomized to receive 1 of 3 financial reimbursements for attendance in ECHO sessions

3.3 Study Duration, Enrollment and Number of Subjects

Each subject's participation will last six months (nine months for subjects who did not complete as of 3/9/2020 due to the complex practice environment experienced by providers during the start of the COVID-19 pandemic).

The entire study is expected to last up to two years.

Total number of subjects will be up to 80 as needed to achieve at least 20 subjects in each of the 3 financial reimbursement groups.

3.4 Study Population

Inclusion Criteria

1. Licensed practicing Primary Care Provider (MD, DO, PA, NP)
2. Currently practicing in NC, not currently participating in ECHO MAT

Exclusion Criteria

1. Another member of the same practice is already enrolled in the study (one provider per practice in Phase 2)
2. Active participation in The University of North Carolina at Chapel Hill (UNC) ECHO Collaborative at beginning of study

4 STUDY PROCEDURES (what will be done)

Once a provider is enrolled a schedule of weekly online live UNC ECHO clinic sessions will be sent from the UNC ECHO study team. Attendance is noted at each session and a summary of the prior months' attendance record is sent to the Principal Investigator monthly, indicating the number of hours spent in training and the reimbursement for those sessions. The appropriate dollar amount will be paid to the participant through a reloadable Visa gift card.

4.1 Subject Completion/ Withdrawal procedures

A primary care provider (subject) can participate in as many or as few ECHO MAT sessions as they like during the six-month enrollment in the Nudges study (nine month enrollment for participants who do not complete as of 3/9/2020), and can continue to participate in ECHO MAT even after completing the Nudges enrollment period. Nudges enrollment is based only on time since initial enrollment. A subject may withdraw (or be withdrawn) from the Nudges study for any reason. The reason for subject withdrawal from the study will be recorded.

5 STUDY EVALUATIONS AND MEASUREMENTS (how measurements will be made)

See Table 1 in Appendix.

6 STATISTICAL CONSIDERATIONS

6.1 Statistical Methods

In Aim 1, we anticipate starting with a random selection of 600 providers from the list of eligible NC providers received from the NC Board of Medicine and NC Nursing Board, limiting to primary care providers identified as primary care through their provider type, which gives more than 90% power to detect a ten percentage point difference in the binary outcome, response to study recruitment. We will use binary models (logit, linear probability models) to examine response to recruitment as a function of study arm, controlling for provider type and county fixed effects.

For Aim 2, we will randomly recruit at least 60 enrollees (and up to 80 to enroll at least 20 providers per arm of this phase). The outcome to be monitored for Aim 2 is the number of ECHO sessions attended in the 6 months following randomization. Because this is a pilot study, the sample size is not powered for the primary outcome, number of ECHO clinics attended. We will conduct a negative binomial or other count data model (depending on statistical tests) of the number of sessions as a function of financial incentive arm to estimate the effect of financial incentives on participation.

